Analyses were computed using Predictive Analytics SoftWare (PASW, Version 25.0). To test whether the groups differed in their baseline scores on the scales and whether there were differences between participants who did and did not complete Time 2 assessments, two-way ANOVAs were performed. To examine improvement in the outcomes (SQoL, FEIT, Faux Pas task, SSPA, and AIHQ), mixed repeated measures ANOVAs were used with time (pre, post) and group (SCIT, TAFT, and TAU) as factors. A mixed repeated-measures ANOVA allows for an examination of the extent to which participants improved over time regardless of group, as well as whether they improved significantly more over time in one group versus the other (group-time interaction). To assess the overall effect sizes, partial eta squared (η^2) was computed with $\eta^2 = .01$ indicating small, $\eta^2 = .059$ medium, and $\eta^2 = .138$ large effects (37). In case of a significant effect, a paired two-sample t test was conducted for each group comparing preand post-results. Effect sizes of paired tests were reported with Cohen's d (37) with $d = .2$, indicating small; $d = .5$, medium; and $d = .8$ large effects. To examine whether the therapeutic alliance was associated with the change in the research variables, we performed a multiple regression, with the difference in each variable (difference between time 1 and time 2) as the dependent variable, and group (0-SCIT, 1-TAFT) and the four dimensions of the therapeutic as the independent variables.

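### Arm-level Cohen's d is specified only after a significant ANOVA effect, which can inflate it when power is low or moderate and leaves the other outcomes without any arm-level change

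*Combined protocol and SAP*

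**What the plan says.** All the relevant text is in the Statistical Analysis section of the combined protocol and SAP. For the five named outcomes, none marked as primary, "mixed repeated measures ANOVAs were used with time (pre, post) and group (SCIT, TAFT, and TAU) as factors". The section then sets out three kinds of estimate.

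- **Overall size.** "To assess the overall effect sizes, partial eta squared" was computed. No significance condition is attached.
- **Arm-level tests and d.** "In case of a significant effect, a paired two-sample t test was conducted for each group comparing preand post-results". The next sentence begins "Effect sizes of paired tests were reported with" and names Cohen's d, so d falls under the same condition.
- **Alliance regression.** A multiple regression is set up "with the difference in each variable (difference between time 1 and time 2) as the dependent variable, and group (0-SCIT, 1-TAFT"), with the four alliance dimensions as further predictors. It carries no significance condition and leaves out TAU.

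The section does not say whether the time effect, the interaction or either one counts as the significant effect. It does not promise arm means, mean changes, between-arm differences or confidence intervals for any outcome, and it does not say that descriptive results are withheld. No sample size, alpha, SD or expected effect is given.

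**The concern.** The background section asks whether any positive change can be credited specifically to SCIT, and says that both therapies were compared with TAU. Answering that takes a signed estimate for each arm and a SCIT-versus-TAU contrast, for every outcome.

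Under the stated rule, whether an arm-level d exists depends on the same data that determine its value. With limited power, an omnibus effect tends to reach significance in those samples where chance made the driving arm look better than it is. The d values that get reported can then overstate how well SCIT works. Outcomes that miss significance offer no arm-level figure to set beside them, and anyone pooling these results would inherit the imbalance. This is so even if every test is valid, and it does not depend on which ANOVA effect is meant to open the follow-up.

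**Working it through.** The plan states no design figure that could be reproduced. The check has two parts: what the text leaves for each outcome, and how much the filter can move d.

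**1. What each outcome receives under the plan**

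| Quantity | Significant effect | No significant effect |
|---|---|---|
| F, p, partial eta squared | yes | yes |
| Paired test and Cohen's d, all three arms | yes | not specified |
| Alliance-adjusted SCIT-versus-TAFT coefficient | yes | yes |
| SCIT-versus-TAU difference in change | not specified | not specified |

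**2. Why partial eta squared does not fill the gap**

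With n per arm, the interaction test is a one-way F on change scores: F = n × (variance of the three mean changes) / (pooled variance of change). Partial eta squared is 2F / (2F + 3(n − 1)).

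Take n = 25 and pooled variance 1 (both assumed), with mean changes of 0.3, 0 and 0 in SCIT, TAFT and TAU. The grand mean is 0.1 and the sum of squares is 0.04 + 0.01 + 0.01 = 0.06, so the variance is 0.03. Then F = 25 × 0.03 = 0.75 and eta squared = 1.5 / (1.5 + 72) = 0.020. Mean changes of −0.3, 0, 0 (SCIT worsens) or 0, 0.3, 0 (only TAFT improves) give the same 0.020.

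**3. How much the filter can move the SCIT d**

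Assumptions, none from the documents: normal change scores with SD 1, three equal arms, d = mean change / SD of change, and p < .05 on the interaction F with (2, 3(n − 1)) df. Results are from 20,000 to 60,000 simulated trials per setting.

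The fair reference is the unfiltered mean of d, not the true value, because d has an ordinary small-sample bias that the fix would not remove. The unfiltered mean is about (true d) / J, with J = 1 − 3/(4(n − 1) − 1). So the ratio to the unfiltered mean is the ratio to the truth times J.

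Example, 25 per arm, true 0.3 in SCIT and 0 elsewhere: the interaction is significant in about 17% of trials, and the mean SCIT d in those trials is 0.54. That is 0.54/0.30 = 1.8 times the truth and 0.54/0.31 = 1.7 times the unfiltered mean.

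Each cell shows the ratio to the truth, then the ratio to the unfiltered mean (no change in TAFT or TAU):

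| n per arm | J | true 0.3, interaction | true 0.5, interaction | true 0.3, interaction or time |
|---|---|---|---|---|
| 20 | 0.960 | 1.92, 1.84 | 1.43, 1.37 | 1.79, 1.72 |
| 25 | 0.968 | 1.79, 1.73 | 1.34, 1.30 | 1.67, 1.62 |
| 30 | 0.974 | 1.68, 1.64 | 1.27, 1.24 | 1.57, 1.53 |
| 40 | 0.981 | 1.53, 1.50 | 1.18, 1.16 | 1.44, 1.41 |

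At a true 0.8 with the interaction as the condition, the ratio to the unfiltered mean is 1.11 at n = 20, 1.04 at n = 30 and 1.01 at n = 40. At 100 per arm it is 1.17 for a true 0.3 and 1.01 for a true 0.5.

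**4. Other patterns of true change (SCIT/TAFT/TAU), ratio to the unfiltered mean**

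- 0.5/0.2/0, interaction: 1.52 at n = 15, 1.26 at n = 30, 1.14 at n = 50, 1.03 at n = 100. The mean TAU d, truly 0, is pushed down to −0.22 at n = 15 and −0.11 at n = 30. TAFT stays near 0.19 to 0.20.
- 0.3 in every arm: 1.01 to 1.06 if the interaction is the condition. If the time effect is the condition, 1.40 at n = 15 and 1.12 at n = 30.
- 0.2/0.2/0 at n = 20: 1.65 with the interaction, 1.80 if either effect suffices. Admitting the time effect therefore lowers the inflation in the SCIT-only settings above, but not in every setting.

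**5. Without the filter**

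For a true SCIT d of 0.50, the mean reported d is 0.53 at n = 15, 0.52 at n = 30 and 0.50 at n = 100. Only the small-sample bias remains.

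**The case against.** Follow-up tests after an omnibus test are a common convention. The sentence governs tests and does not forbid descriptive tables. The condition applies to the omnibus effect, not to each arm's own test, so once it is met all three arms get a d, including arms that did not change. These points stand. They make this a matter of complete and unbiased reporting and leave the validity of the tests untouched. They do not supply the missing commitment to report arm-level change for every outcome.

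A reader might infer that outcomes missing significance have no effect size or direction at all, or vanish from the effect-size record. The documents do not support that. Partial eta squared is unconditional, and the group coefficient in the alliance regression is a signed SCIT-versus-TAFT contrast in change. That coefficient is adjusted for alliance and omits TAU, so it is only a partial substitute.

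A reader might also infer that the reported d values are systematically too large. That cannot be established without a sample size. The 1.8-fold end of the range comes from a small true effect, no change in the other two arms and low power. With good power the inflation is negligible, and under an interaction condition the TAU d is pushed down, not up.

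**Conclusion.** The concern holds in a limited form. The text makes arm-level d conditional on a significant ANOVA effect. For outcomes that fail the condition, it specifies neither an arm-level change nor a SCIT-versus-TAU difference. That part needs no assumption.

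The bias is a possibility whose size depends on power. With the interaction as the condition, change in SCIT only and 20 to 40 per arm, the reported SCIT d is about 1.8 to 1.5 times its unfiltered mean at a true 0.3, 1.4 to 1.15 times at 0.5, and 1.1 to 1.0 times at 0.8. At 100 per arm it is close to 1.0 for a true 0.5 or more. In these SCIT-only settings it is somewhat smaller if a time effect can also meet the condition. Arm sizes, alpha and true effects are all assumed. A change to the plan is worthwhile because the remedy is cheap and works whatever the true power was.

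**What to change.** Replace the conditional sentence with:

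> For each of the five outcomes and each arm, the mean change (Time 2 minus Time 1), its SD, 95% CI and standardised effect size are reported regardless of the significance of any ANOVA effect, together with the between-arm differences in change and their 95% CIs.

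Significance then governs which claims are made, not which estimates are shown. The cost is one sentence in the plan and a fuller results table, with no new data. Some effect sizes will look smaller than they would under the conditional rule.
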